## **STUDY PROCEDURES**

Data collection includes patient descriptive data as well as three groups of outcomes: geriatric syndromes, medications and health status, safety and healthcare utilization. Table 1 shows a summary of the study timepoints along with the corresponding assessments. Upon enrollment, hospitalized participants complete interviewer-administered questionnaires, which require approximately 45 minutes per participant. Following

discharge to SNF, facility staff is required to assess all residents upon SNF admission and discharge using the standardized Minimum Data Set (MDS), which includes an assessment of these same geriatric syndromes using similar scales. The baseline hospital questionnaires are repeated by research staff via telephone 7-10 days after PAC discharge and in-person in the participant’s place of residence at 90-days after PAC discharge. *(During the COVID-19 pandemic, the VUMC IRB allowed the 90-day visits to be completed as telephone calls or using Vanderbilt’s HIPAA compliant video technology to limit exposure risks to both participants and staff).* A telephone interview is also conducted at 60-days post SNF discharge to assess medications and health-related measures. If a participant has a follow-up outpatient visit scheduled at VUMC during any of these time frames, an effort is made to conduct the interview in-person during that visit, if they prefer. For assessments completed in-person, the study team provided hearing and visual aids if necessary (e.g., hearing amplifiers and large font printed response cards with Likert scale categories). Both the intervention and control groups will be monitored using the same data collection schedule and measures. All interview assessments are completed by trained research personnel on our multidisciplinary team which includes a social worker, geriatric nurse practitioners, clinical pharmacists, geriatrician, hospitalist, and psychologist.

In the event a participant is unable to complete assessments due to delirium or cognitive impairment, their designated surrogate or caregiver (e.g., child, spouse, assisted living facility nurse) is interviewed to complete assessments which are validated for use with surrogates. Assessments that can be completed by surrogates include the ICIQ (urinary incontinence), Determine, falls, pressure ulcers, medication history, and demographics.

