## Schedule of Assessments

**Table 1. Data Collection Schedule**

Measures	Baseline Hospital	SNF*	Post SNF Discharge		
			7-Days Telephone Person	60-Days Telephone	90-Days In- Person
Descriptives					
Demographics and Length of Stay	X	X			
Charlson Comorbidity Index	X				
Adverse Drug Event Risk Score	X				
Walter Index (Life Expectancy)	X				
Patient Attitudes Toward Deprescribing (PATD)	X				
Primary Outcome – Medications					
Total number of Routine & PRN Medications	X	X	X	X	X
Total number of potentially inappropriate medications (PIMs) and medications associated with geriatric syndromes (MAGS)	X	X	X	X	X
Drug Burden Index (DBI)	X	X	X	X	X
Secondary Outcomes – Geriatric Syndromes, Adherence, Functional Health					
Cognitive Impairment (BIMS)	X	X	X		X

Delirium (BCAM)	X	X			X
Depression (PHQ-9)	X	X	X		X
Urinary Incontinence (ICIQ-UI SF)	X	X	X		X
Unintentional Weight Loss (DETERMINE)	X	X	X		X
Pain (Brief Pain Inventory, BPI-short form)	X	X	X		X
Falls	X	X	X	X	X
Pressure Ulcers	X	X			X
Medication Behavior (ARMS)	X			X	X
Functional Health Status (VES-13)	X		X		X

*Safety and Healthcare Utilization Outcomes*

Unplanned Healthcare Utilization (Hospitalizations, emergency room visits)		X	X	X	X
Adverse Drug Withdrawal Events & Adverse Drug Events	X	X	X	X	X
Status: Long-Term Care, Hospice, Death		X	X	X	X

\*Secondary outcome measures at SNF phase were assessed by SNF personnel as part of their routine MDS assessments

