## **Secondary Outcomes - Geriatric Syndromes, Medication Adherence, Functional Health Status**

**Delirium:** The Brief Confusion Assessment Method (bCAM) is a brief screening tool for delirium and has been validated among hospitalized, older patients. If the participant screens positive for delirium, no other participant interviews are conducted at that time. Research personnel continue to re-assess delirium daily during hospitalization; and, when the participant screens negative for delirium via the bCAM, the remaining assessments are administered to the participant. If delirium continues throughout the hospital stay or the participant is otherwise unable or unwilling to complete the assessments, the surrogate is approached for a subset of the geriatric syndrome assessments (i.e., incontinence, nutrition and fall history). The bCAM is not repeated by research personnel at 7-day follow-up because it has limited validity when administered via the telephone; thus, it is repeated only at 90-day follow-up during the in-person home visit. Additionally, PAC personnel use the CAM (i.e., the Confusion Assessment Method, [CAM]), which is a modified version of the bCAM, to assess delirium during the PAC stay via the MDS assessment.

**Cognitive Impairment:** The Brief Interview for Mental Status (BIMS) is a short, validated assessment of cognitive impairment with a total score range from 0 to 15 (0-7: severe impairment; 8-12: moderate impairment; 13-15: cognitively intact). The BIMS is routinely used in the SNF care setting as part of required MDS assessments for all SNF patients upon admission and discharge and following a hospitalization event.

**Depression:** The Patient Health Questionnaire (PHQ) is a validated tool to assess depression symptoms and severity. Each item is scored from 0 (“not at all”) to 3 (“nearly every day”) to yield a total score range from 0 (no depressive symptoms) to 27 (severe depression). In the event that a participant reports severe depression or thoughts of self-harm, the study team elicits more information to evaluate their immediate safety then contacts the primary treatment team to address this with the participant. The PHQ-9 is routinely used in the SNF care setting as part of required MDS assessments.

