Pressure Ulcers: The presence of pressure ulcers (Stages 0 – 4) will be abstracted from the hospital medical record (flowsheets) at baseline and confirmed via direct interview with the patient and/or family. Similarly, this same information will be, again, abstracted from the PAC medical record and confirmed via patient/family interview during an in-person visit 7 and 90-days post PAC discharge.

Adherence to Refills and Medications Scale (ARMS): The ARMS consists of 12 items to assess overall medication adherence, with a total score range of 12 to 48. A lower score is indicative of better medication adherence. Example questions include: “How often do you forget to take your medicines?”, “How often do you miss taking your medicines when you feel better?”, and “How often do you put off refilling your medicines because they cost too much money?” Response options are on a 4-point Likert scale that ranges from “none of the time” to “all of the time.”

Vulnerable Elders Survey (VES-13) is a functional measure of health status that assesses a patient’s cognitive, physical and self-care activities and which also includes an item for self-rated health status. Scores range from 1 to 10, with lower scores indicative of better health.

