Hypothesis 2a: The prevalence and severity of geriatric syndromes will be analyzed at each time point following SNF discharge. The effects of intervention on the prevalence of each type of geriatric syndrome will be assessed using mixed-effects logistic regression, adjusting for measurement time point (categorical). The severity of each geriatric syndrome is measured on an ordinal scale. Thus, severity will be analyzed using mixed-effects proportional odds logistic regression, also adjusting for measurement time point. For either method, the correlation among repeated measures will be modeled using a random intercept term indexed by subject. The effects of intervention at each time point will be summarized using the odds ratio with Wald-type 95% confidence intervals. Statistical significance will be indicated when the 95% confidence interval excludes the value one (i.e., null hypothesis value for both types of logistic regression). Model fit diagnostics and alternative analysis strategies will be considered as described for Hypotheses 1a-1c.

Hypothesis 2b: Patient medication adherence will be measured using selected questions from the ARMS, based on an ordinal scale. Functional health status will be measured using the VES-13 total score, which is also an ordinal outcome. The effects of intervention on these outcomes will be assessed at 7 and 90-days following SNF discharge using mixed-effects logistic regression or proportional odds logistic regression in a manner that is analogous to that described for Hypothesis 2a.

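### The 7-day pressure-ulcer assessment conflicts with the visit schedule, and delirium, measured once after SNF discharge by a positive/negative screen, does not fit the stated mixed-effects and severity models

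*Combined protocol and SAP*

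**What the plan says.** **Pressure ulcers.** Descriptions of Assessments (Secondary Outcomes) has ulcer status abstracted from records, graded Stages 0 to 4, and "confirmed via patient/family interview during an in-person visit 7 and 90-days post PAC discharge". Study Procedures has the baseline questionnaires "repeated by research staff via telephone 7-10 days after PAC discharge" and in person at 90 days. It also allows a follow-up interview to be held in person if a VUMC outpatient visit falls in the window and the participant prefers that. The Table 1 row reads "Pressure Ulcers X X X"; the three marks stand under baseline, SNF and 90 days, and the 7-day and 60-day cells are empty.

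**Delirium.** The Table 1 row reads "Delirium (BCAM) X X X", with the marks in the same three columns. The text agrees: the bCAM is left out at 7 days because it is not considered valid enough by telephone, "thus, it is repeated only at 90-day follow-up during the in-person home visit". It is described as a screen with a positive or negative result.

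**Analysis.** Statistical Considerations, Outcomes, Hypothesis 2a covers the assessments after SNF discharge. Prevalence is modelled by mixed-effects logistic regression and severity by mixed-effects proportional odds, both with categorical time, and "the correlation among repeated measures will be modeled using a random intercept term indexed by subject". It also states: "The severity of each geriatric syndrome is measured on an ordinal scale". Data Analyses (Repeated measures) provides an unnamed alternative with sandwich standard errors if a mixed model cannot be implemented.

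**The concern.** There are two separate problems.

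The first is operational. Staff who follow the text would collect a 7-day ulcer assessment; staff who follow Table 1 would not. The analysis data set then has either one or two ulcer values per person after SNF discharge, and the plan does not say which.

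The second is statistical. A random intercept describes how repeated values from one person resemble each other. With a single binary value per person nothing in the data informs its variance, and a time effect has no second time to be compared with. Any odds ratio reported from such a model depends on the variance the software happens to settle on. For delirium, the severity analysis also needs an ordinal grade that the plan never defines. At stake are the choice of model after the data are seen and an uninterpretable estimate for a syndrome named in Hypothesis 2a.

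**Working it through.** **Step 1. The 7-day contact, place by place.**

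| Place | Mode at day 7 | Ulcers at day 7? |
|---|---|---|
| Descriptions of Assessments, Pressure Ulcers | in person | yes |
| Study Procedures | telephone; in person only at a coinciding outpatient visit | not stated |
| Primary Outcomes, Total number of Medications | call | not stated |
| Delirium paragraph | telephone, given as the reason to omit the bCAM | not stated |
| Table 1 | column header not readable with certainty | no mark |

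The pressure-ulcer text implies 2 assessments after PAC discharge (7 and 90 days). Table 1 gives 1. The text's count is not reproduced by the schedule.

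**Step 2. Marks after SNF discharge in Table 1, by syndrome.** Cognition, depression, incontinence, weight loss and pain: 2 each. Falls: 3. Delirium: 1. Pressure ulcers: 1. That makes eight syndromes.

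**Step 3. The logistic model with one value per person.** Let x = 0 for control and 1 for intervention, with no time term because time is constant:

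P(Y = 1 | x) = ∫ expit(α + βx + σz) φ(z) dz

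The data supply two proportions, and the model has three unknowns (α, β, σ). For each σ some pair (α, β) reproduces both proportions exactly, so the maximised likelihood is the same for every σ.

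Inputs: 420 participants with 90-day data (Sample Size and Randomization), so 420 / 2 = 210 per arm. As a side check, 576 × (1 − 0.275) = 417.6, close to the stated 420. The documents give no 90-day delirium prevalence, so three control-versus-intervention pairs are assumed.

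For 15% vs 10%, the maximised log-likelihood is 210 × [0.15 ln 0.15 + 0.85 ln 0.85 + 0.10 ln 0.10 + 0.90 ln 0.90] = 210 × (−0.74779) = −157.036. At σ = 0 the odds ratio is (0.10/0.90) / (0.15/0.85) = 0.630. With σ fixed at other values (Gauss-Hermite quadrature):

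| Assumed prevalence | log-likelihood, every σ | OR σ=0 | σ=0.5 | σ=1 | σ=2 | σ=3 |
|---|---|---|---|---|---|---|
| 10% vs 5% | −109.956 | 0.474 | 0.467 | 0.446 | 0.366 | 0.276 |
| 15% vs 10% | −157.036 | 0.630 | 0.622 | 0.597 | 0.514 | 0.423 |
| 30% vs 20% | −233.366 | 0.583 | 0.569 | 0.532 | 0.430 | 0.331 |

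The same data yield any of these odds ratios with equal support.

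**Step 4. Severity.** A positive/negative screen has two levels. A proportional odds model on two levels is the logistic model again, so the delirium severity analysis adds nothing to the prevalence analysis. Ulcer Stages 0 to 4 are ordinal, so the scale suits the model.

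**Step 5. Ulcers if only the 90-day value exists.** Presence behaves as in Step 3. For stage, with an assumed control distribution of 85/5/5/3/2% and a true log-odds shift of 0.6 (σ = 0), the log-likelihood falls only from −217.456 at σ = 0 to −217.491 at σ = 3, a change of 0.035. Over that range the odds ratio for a lower stage goes from 1.82 to 2.94. So σ is practically unidentified here too, while the ordinary model (σ = 0) can be fitted. If the 7-day value exists as well, there are two values per person and the stated model can be fitted.

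**The case against.** The strongest reply is that the plan already covers the modelling problem. Data Analyses provides for an alternative method, and Hypothesis 2a says that alternative strategies will be considered. Dropping the constant time term and the random intercept leaves ordinary logistic or proportional odds regression, still with an odds ratio and Wald interval. That is the natural fallback, and it limits the harm. But the plan names no method, and its trigger is that a mixed model cannot be implemented. Software may return an estimate without signalling that the variance is arbitrary, so the trigger may never be pulled. Sandwich standard errors neither create a delirium severity grade nor settle when ulcers are assessed.

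A reader might also go further than the documents allow, in three ways.

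- One might infer that no in-person 7-day contact exists at all. Study Procedures permits one at a coinciding outpatient visit, and the Table 1 column header is too garbled in the available text to decide the matter. What is missing is an in-person 7-day visit scheduled for all participants.
- One might infer that the severity model is wrong for pressure ulcers as well. It is not: Stages 0 to 4 are ordinal, and only the repeated-measures terms can fail.
- One might count two of eight syndromes as affected outright. The second holds only if Table 1 is the correct schedule, which the documents do not settle.

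**Conclusion.** The point stands in limited form. The pressure-ulcer text disagrees with Table 1 on whether there is a 7-day assessment, and with Study Procedures on its mode. Delirium has one value after SNF discharge in both text and table, so its schedule is consistent and only its analysis is at fault: the random-intercept variance is not identified, the time term is empty, and no severity grade is defined.

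One of eight syndromes is affected for certain. Pressure ulcers are a second if Table 1 is right, and then for the time and random-intercept terms only.

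That the variance is not identified does not depend on the assumed prevalences; the particular odds ratios do. It does rest on reading Hypothesis 2a as it is written, with only the values after SNF discharge as outcomes. These are secondary outcomes. The primary medication-count analysis and the sample size are not touched.

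**What to change.** **Schedule.** Reconcile Study Procedures, Table 1 and the pressure-ulcer paragraph. Either ask about ulcers in the 7-day call, mark the 7-day cell in Table 1 and remove the in-person wording for day 7, or delete day 7 from the paragraph. If the 7-day contacts are already complete, state what was collected and correct the text to match.

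**Delirium.** In Hypothesis 2a, specify ordinary logistic regression for the 90-day bCAM, adjusted for baseline bCAM, and exclude delirium from the severity models. Define baseline as the first reading, since a positive screen is repeated daily in hospital. State how a 90-day bCAM obtained remotely is handled: Study Procedures allowed telephone or video visits during COVID-19, and the delirium paragraph doubts the telephone bCAM.

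**Ulcers, if only the 90-day value exists.** Use ordinary logistic regression for presence and ordinary proportional odds for stage, without the time and random-intercept terms. With two values, keep the stated model.

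**Cost.** A few lines of text and, under the first schedule option, one question in an existing call. Ulcer data from a call are reported by the participant or surrogate. Baseline adjustment sets delirium apart from the other syndromes, for which Hypothesis 2a names none, so the reason should be stated.

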### **Safety and Healthcare Utilization Outcomes**

Unplanned Healthcare Utilization and Patient Status: We will request a release of healthcare information as part of our consent, which will provide permission to track healthcare utilization (ER visits, hospitalizations) at VUMC or elsewhere during the study period. We will contact the PAC care providers weekly during each participant’s PAC stay to track their status and will follow-up 7, 60, and 90 days after PAC discharge with each participant. If a participant has been moved to hospice care, they will be withdrawn from the study.

Adverse Drug Withdrawal Events (ADWEs): Any unplanned healthcare utilization event (i.e., acute hospitalization, emergency room visit) will be assessed by blinded physician co-investigators for ADWEs. This assessment will include validated scales such as the Naranjo. A detailed description of the adjudication procedures can be found in the *Safety Assessments* section of this protocol.

[figure not shown]

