## PAC Handover and Ongoing Deprescribing at PAC Facility

Within 24-hours of transition to PAC, a study pharmacist or NP has a phone conversation with a designated PAC provider with prescribing authority (NP or physician) to review the Transfer Medication List, highlight deprescribed medications and the need for medication-specific monitoring. In addition, all medications recommended for deprescribing may not be stopped prior to hospital discharge in the interest of first monitoring symptoms and ensuring safety or due to delayed contact and input from the outpatient prescriber. Medications for additional deprescribing at the PAC may be highlighted during this initial handover and discussed again in weekly follow-up calls while the patient remains in PAC (Phase 3).

Following PAC handover, we initiate a weekly conversation via telephone with the designated PAC provider to review intervention participants' medication administration record (MAR) and any drug withdrawal events. Reasons for modifying the Transfer Medication List during the PAC stay will be discussed and intervened upon as necessary. The intervention also will continue for participants readmitted to VUMC directly from PAC (estimated 20%) and continue upon transfer back to the PAC. The study PharmD or NP may also continue to communicate with the original prescriber/ outpatient provider during the PAC stay to confirm their agreement with medication changes. At the time of discharge from the PAC facility, a final reconciled medication list will be sent to the patient's primary outpatient providers along with suggestions for continued medication management and deprescribing as well as any explanations for other medication changes made.

For analytical and feasibility purposes, the intervention ends at the point of discharge to home. If a patient discharges to home instead of a partner PAC facility, they will be withdrawn from the study and only considered to have one phase of the intervention. For safety reasons, the study team provides their outpatient provider with the final discharge medication list highlighting any symptom monitoring required.

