### Interim analyses and Stopping Rules

Interim analyses will be conducted to evaluate safety endpoints but will not be conducted to evaluate conditional power (futility) or to assess efficacy.

Safety is evaluated by examining group differences in death and serious adverse events semi-annually in conjunction with scheduled DSMB meetings to evaluate the safety of the study intervention, and the associated risk-to-potential benefit ratio. The Principal Investigators will address study efficacy only at the end-of-study, and thus will not consider terminating the trial early on the basis of conditional power (futility) or evidence of efficacy. This is because firm evidence will be required to change current clinical practice, and because trials that have stopped early for efficacy often report implausibly large effect sizes (and therefore should be considered with skepticism). At the conclusion of each DSMB meeting, the Board should take into account the statistical evidence (as summarized by the relative hazard of safety endpoints and the corresponding 95% confidence interval) as well as practical and clinical considerations to make one of the following recommendations based on safety:

1. Suspend enrollment due to safety concerns secondary to study intervention including:

- a. A difference in all-cause mortality between patients randomized to the deprescribing intervention versus usual care such that the DSMB deems the difference to be study-related and excessive.
  - b. A difference in drug related SAEs between patients randomized to the deprescribing intervention versus usual care such that the DSMB deems the difference to be study-related and excessive.
2. Continue enrollment

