## Safety Analyses

All-cause mortality will be quantified by the count of deaths per person-months (28 days) of observation by intervention/usual care group. These values will be computed overall and stratified by study phase. Thus, the maximum follow-up period for mortality (and other safety outcomes) is 90 days after SNF discharge. Cox proportional hazards regression will be used to quantify statistical uncertainty about the effect of intervention on

the hazard of death (overall and separately within study phase), which will be summarized using the hazard ratio and corresponding Wald-type 95% confidence interval.

The incidence and timing of (potentially recurrent) adverse events will be quantified, for each type of event both overall and stratified by study phase, by counting the number and fraction of affected participants, by tabulating the number of events per participant, and the total number of events per person-months. The effect of the intervention on the hazard of each adverse event type (overall and separately within study phase) will be quantified using Cox proportional hazards regression in a recurrent events (frailty) configuration, which accounts for between-subject heterogeneity in the baseline hazard of recurrent events. In other words, this approach accounts for the within-subject correlation among recurrent event times. The hazard ratio will be summarized using a Wald-type 95% confidence interval.

If there are sufficiently many events, the Nelson-Aalen estimator of the baseline hazard will be used in conjunction with the estimated hazard ratio to estimate median survival with Wald-type 95% confidence interval, for each type of adverse event. Graphical regression diagnostics will be used to evaluate model fit and modeling assumptions of the Cox proportional hazards method.

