## Data Analyses

Missing Data: We have extensive preliminary data describing attrition due to mortality which should not differ between the intervention and control groups. However, we cannot exclude the possibility that missing data will be associated with intervention. We will examine the incidence of missing data by group. If imbalances are found, we will implement a series of sensitivity analyses, using multiple imputations, to assess the degree of bias that might be induced by missing data.

Randomization, intent-to-treat, and safety outcomes: Participants will be assigned to the usual care control group or the intervention group in a completely randomized fashion (i.e., without blocking or stratification). The effectiveness of randomization will be assessed by summarizing the balance of baseline demographic and clinical factors across randomization groups. The sample mean, standard deviation, and five-number summary will be used to summarize continuous variables. The count and proportion will be used to summarize categorical variables. All randomized patients who complete Phase 2 (i.e., discharged to a partner SNF) will be included in analyses. We will implement both intent-to-treat and per-protocol analyses.

Repeated measures: Barring study withdrawal or death, each participant will be assessed at multiple time points. We anticipate that such repeated measurements will exhibit correlations across time points. Our statistical plan takes full advantage of this information by using a mixed-effects framework for each analysis. In the event that a mixed-effects technique cannot be implemented, an alternative method will be used and the standard errors of effect estimates will be adjusted using the Huber-White ‘sandwich’ method.

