## Meeting Processes and Outcomes

Meetings are closed to the public because discussions may address confidential participant data. All Closed Session Meetings have an open session attended by the Board members, study investigators and NIA Program Official prior to and immediately following the Closed Session. The Closed Session will be attended by only the Board members, NIA Program Official and unblinded study biostatistician. The DSMB also has an option to hold an Executive Session attended exclusively by the DSMB members.

Following the initial meeting, the DSMB will meet at least twice a year to review blinded or unblinded data as needed and appropriate, including data on recruitment, randomization, compliance, retention, protocol adherence, intervention effects, gender and minority inclusion, and subject safety. The reports list and summarize safety data (adverse events) and describe the status of the study (e.g., participants screened, enrolled, completed, and discontinued). The DSMB is responsible for identifying problems related to safety (including all SAEs/SUSARs), requesting additional data relevant to safety (including all SAEs/SUSARs), proposing analyses of safety endpoints as needed, and considering the rationale for continuation of the study in light of safety data, progress of randomization, retention, protocol adherence, and data management. Reports of SAEs and SUSARs for two interim looks at the data will initially be provided to the DSMB in a blinded fashion (i.e., treatment group assignment will not be revealed), but the DSMB will retain the right to request an unblinded report. Only DSMB members will have access to unblinded data in order to preserve the integrity of data and minimize potential for bias while maintaining appropriate safety monitoring.

After each DSMB meeting, the chairperson will provide a written report including any formal recommendations to the PIs and the NIA program official. In turn, the PIs will provide all reports to the Vanderbilt IRB. Each meeting must include a recommendation to continue or terminate the study and whether the DSMB has any concerns about participant safety made by a formal DSMB majority or unanimous vote. A recommendation to terminate the study may be made by the DSMB at any time by majority vote. The Chair should provide such a recommendation to the NIA immediately by telephone and email.

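### Hospice entry triggers study withdrawal, and the plan does not say that deaths after it are still collected and counted in all-cause mortality

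*Combined protocol and SAP*

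**What the plan says.** Under Safety and Healthcare Utilization Outcomes, the protocol states: "If a participant has been moved to hospice care, they will be withdrawn from the study". It names nothing that continues after that withdrawal.

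Under Safety Analyses, "All-cause mortality will be quantified by the count of deaths per person-months (28 days) of observation by intervention/usual care group", with a Cox model for the hazard of death, overall and within study phase. The only limit on time is that "the maximum follow-up period for mortality (and other safety outcomes) is 90 days after SNF discharge". Hospice, withdrawal and censoring are not mentioned there.

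Under Data Analyses, the repeated-measures paragraph makes withdrawal, like death, an end to a participant's assessments. The same section sets the analysis population: "All randomized patients who complete Phase 2 (i.e., discharged to a partner SNF) will be included in analyses". A participant who reached a partner SNF and later entered hospice therefore stays in the analysis. What is undefined is when that person's follow-up ends.

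Under Interim analyses and Stopping Rules, one ground for suspending enrollment is "A difference in all-cause mortality between patients randomized to the deprescribing intervention versus usual care", if the DSMB judges it study-related and excessive.

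**The concern.** Hospice entry is closely tied to prognosis. The plan's own eligibility screen uses it as a search term for a life expectancy below six months. If observation stops there, the Cox model censors participants just as their risk of death rises, and its assumption that censoring is unrelated to prognosis fails.

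No other safety measure fills the gap. Safety Monitoring and Assessments counts a death as an adverse event only if the patient was not receiving hospice services, and the section on review of unplanned utilization and deaths draws the same line. A death under hospice care therefore gets no adverse event review of its own, and all-cause mortality is the measure left to record it.

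Two analysts following the text could count different deaths. If the withdrawal were applied literally during the trial, the deaths might never be collected, and no later analysis choice could recover them. The missing-data paragraph offers multiple imputation if imbalances appear, but it does not define who remains under observation for mortality.

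**Working it through.** **Figures in the plan.** The plan gives no mortality rate, hospice rate, event count or power for mortality, so there is no mortality figure to reproduce. The nearest figure is attrition, under Sample Size and Randomization: 576 × (1 − 0.275) = 417.6, against 420 stated, which agrees within rounding. The 27.5% pools death with other loss and does not separate hospice, so it cannot size this point.

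**Which sections bear on deaths after hospice entry.**

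- Towards loss: the withdrawal rule itself; the end of assessments at withdrawal (Data Analyses); person-time defined by observation (Safety Analyses).
- Towards capture: Table 1 lists hospice and death as status items from the SNF stay to 90 days; the notification section monitors deaths for participants across phases, with alerts from the medical center record; the reporting section sends every participant death to the project officer.
- Neutral: the handover section uses the same withdrawal wording for another group ("If a patient discharges to home instead of a partner PAC facility, they will be withdrawn from the study") and adds a step ("For safety reasons, the study team provides their outpatient provider with the final discharge medication list"). That is a one-time communication. It says nothing about counting deaths in either group.

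The capture items are rules for collection and reporting. None addresses a withdrawn participant, and none is an analysis rule.

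**Effect on the mortality ratio under the literal reading (assumed inputs).** Let h1 and h0 be the shares of deaths that follow hospice entry in the intervention and control arms. If those deaths are not counted,

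counted ratio ≈ true ratio × (1 − h1)/(1 − h0).

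- Equal shares: (1 − h)/(1 − h) = 1, so the ratio is unchanged. The log-scale confidence interval widens by 1/√(1 − h): 1/√0.8 = 1.118 at h = 0.2 and 1/√0.5 = 1.414 at h = 0.5, that is 12% to 41% wider.
- Illustration with unequal shares and a true ratio of 1.00: h1 = 0.4, h0 = 0.3 gives 0.6/0.7 = 0.857; h1 = 0.3, h0 = 0.4 gives 0.7/0.6 = 1.167.

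The formula ignores the person-time removed with those deaths. A simulation that censored at hospice entry gave 0.856 to 0.861 and 1.163 to 1.172 for the same two cases, so the shortcut is adequate. It assumed a 117-day window (26.9-day mean stay plus 90 days), 6% to 14% mortality, a mean of 20 days from hospice entry to death, and 2% of survivors in hospice. It checks the formula and is not evidence about the shares.

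**The case against.** The strongest reply is that the documents lean towards capture. The outcome is named all-cause mortality with no hospice exception, the record alerts need no contact with the participant, and the split between hospice and other deaths presupposes that the team learns of both. The withdrawal sentence follows directly on utilization tracking and follow-up contacts, so it can be read as ending those and not death surveillance. This stands as far as it goes: many of these deaths would probably become known. But the alerts cover the medical center's own record, and knowing of a death does not settle whether it, and the person-time before it, enter the analysis.

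The consequence is also limited. Hospice-eligible patients and those with a life expectancy under six months are not enrolled. Acute care before hospice entry is still seen as an adverse event. The DSMB has no numeric boundary and its remit includes "proposing analyses of safety endpoints as needed". Sampling error matters too: with an assumed 25 counted deaths per arm, the standard error of the log ratio is √(2/25) = 0.28, giving a 95% interval around 1.00 of about 0.57 to 1.74. A shift to 0.86 (ln 0.857 = −0.154) is about half a standard error. All of this stands, and it is why the point is a cheap improvement and not a serious flaw.

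A reader might go further and infer that hospice deaths will certainly be lost, or that the mortality comparison is biased in favour of the intervention. The documents support neither: the capture rules point against certain loss, and nothing suggests that hospice use will differ by arm. Nor do hospice patients leave the analysis population if they reached a partner SNF.

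**Conclusion.** The point holds as a gap between a stated withdrawal rule and the mortality analysis. Taken literally, the rule would informatively censor a measure that the DSMB uses, and no section says that surveillance continues after withdrawal or that the later deaths are analysed.

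The size and direction of any bias cannot be known from the documents. With equal hospice entry by arm, the ratio is about unchanged and the loss is one of precision. The 0.86 or 1.17 illustration rests wholly on assumed shares of 30% and 40%, and on complete loss of the deaths after hospice entry. The case for acting is that the change is small and that deaths left uncollected cannot be restored later. Figure 1 and the consent pages are not in the text available, so this conclusion does not rest on what they may say.

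**What to change.** 1. **Safety and Healthcare Utilization Outcomes.** Limit the hospice withdrawal to the intervention and the interviews. Add: *Unless consent is withdrawn, the date of hospice entry and vital status are still collected to the end of the mortality window.*
2. **Safety Analyses.** State that deaths from any cause, including under hospice care, and the person-time up to them count in the mortality rate and the Cox model.
3. **End of follow-up.** The window is anchored to SNF discharge, so a participant who has no such date has no defined end. For those participants, pre-specify an end date that does not depend on hospice entry, for example a fixed interval from randomization or hospital discharge, the same in both arms. An interval counted from hospice entry would tie the window to a post-randomization event linked to prognosis, and should be avoided.

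The cost is a few sentences and a vital-status check for the few hospice patients whose death is not flagged in the medical center record. The team must also confirm that the consent and the records release cover this. Enrollment Procedures describes access to outside records for safety monitoring, and the utilization section names emergency visits and hospitalizations. Neither mentions follow-up after withdrawal. Clinical care in hospice is not affected.
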